### **Hypotheses of Equivalence and Superiority (Secondary Endpoints)**

The secondary endpoints will be evaluated in the same way as the primary endpoint, but will be considered as supportive information.

## **6. ANALYSIS SUBSETS**

### **6.1 Run-in Population**

The run-in population includes all subjects who make at least one application of placebo gel in the run-in period of the study.

### **6.2 Randomized Population**

The randomized population consists of all subjects who were randomized.

### **6.3 Safety Population**

A safety population subject is any individual who was randomized into the study and has evidence of usage of at least one dose of the randomized investigational product according to subject's diary. For subjects who were randomized but fail to return their diary and for whom no evidence of study drug use is thus available, the following conservative approach will be applied:

- if some safety or efficacy data for these patients is available after Visit 3, they will be included in the safety population;
- if no safety or efficacy data for these patients is available after Visit 3, they will be considered lost to follow-up and excluded from the safety population.

The safety population will be the primary population for the safety analysis. Analyses on the safety population will be based on actual treatment received, as determined by kit schedule.

### **6.4 Intent to Treat Population (ITT Population)**

Following the intent-to-treat principle, the ITT population includes all randomized subjects. Analyses on the ITT population will be based on randomized treatment, as determined by randomization schedule. This population will be used for sensitivity analysis of both equivalence and superiority, LOCF method will be used for imputing missing data.

## **6.5 Modified Intent to Treat Population (mITT Population)**

The mITT population includes all Safety population subjects who met all inclusion/exclusion criteria and return for at least one post-baseline evaluation of WOMAC Pain Subscale.

Subjects who discontinued early and have at least one post-baseline efficacy evaluation will be included in the mITT population using LOCF. This population will be used for testing superiority. Analyses on the mITT population will be based on randomized received, as determined by randomization schedule.

## **6.6 Per Protocol Population (PP Population)**

The Per Protocol (PP) population includes all mITT subjects who:

- met all inclusion/exclusion criteria
- apply 75% to 125% (both inclusive) of the scheduled applications of the assigned product
- return for the 4 week evaluation of WOMAC Pain Subscale score within the visit window (+/- 4 days; i.e., study Day 24-32) or discontinue from the study due to treatment failure (included as treatment failures)
- have no major protocol deviations impacting the primary efficacy outcome measure.

These major protocol deviations are described in [section 7.9](#). The list of protocol deviations which lead to exclusion of subjects from the PP population will be finalized at the Blind Data Review (BDR) meeting to be held prior to database lock.

This population will be used for testing the clinical equivalence.

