	
who meet all inclusion/exclusion criteria, receive study treatment, and return for at least one post-baseline visit.
 
• Safety (SAF) population: All randomized subjects who receive at least one study treatment. 
Note: Patients discontinuing early from the study due to lack of treatment effect will be included in the PP population, using Last Observation Carried Forward (LOCF). Subjects discontinuing early for other reasons will be excluded from the PP population, but will be included in the mITT population, using Last Observation Carried Forward (LOCF).

Ethical Issues	The study will commence only after a written approval is obtained from the Institutional Review Board for the submitted protocol, ICD and other relevant documents. The study will be conducted as per the ICMR Ethical Guidelines for Biomedical Research on Human Subjects (2006), ICH-GCP Guidelines and in accordance with the Declaration of Helsinki (Fortaleza, Brazil, October 2013).

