7.10 Treatment Compliance

A Subject Diary will be provided to all subjects where it is required to document the date and time of application of the medication. In the subject diary, subjects will also note of any adverse event observed, date and time of rescue medication administration and any concomitant medication taken or changed.

Compliance will be determined from the subject diary, which the subject will be trained and instructed to use to record all doses, as well as all missed doses. The number of missed and additional doses will be captured on the compliance page of the eCRF.

The used study medication tubes will be returned to the study site at appropriate visits or early termination or as applicable.

Subjects who are not compliant with application will be re-c counseled during the study visits.

Subjects who will take less than 75% (<84 applications) of total study drug during the study will be considered non-compliant and discontinued from the study. Subjects who will take more than 125% (>140 applications) of study drug are also considered non-compliant and the same subjects will not be considered for the Per-protocol (PP) population.

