12.2.3 Per-Protocol Population (PP)

The per-protocol population (PP) includes

1. The per-protocol population will be the definitive population for equivalence analysis.

2. All randomized subjects who meet all the inclusion/exclusion criteria.
3. Completed study in compliance with the protocol.
4. Administered a pre-specified proportion of the scheduled doses (e.g., 75% to 125%) of the assigned product for the specified duration of the study.
5. Returned to the study site for the primary endpoint visit within the specified window (+/- 4 days) OR discontinued from the study as a treatment failure.
6. Subjects discontinued early from the study due to lack of treatment effect should be included in the PP population, using Last Observation Carried Forward (LOCF).

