#### **7.12.2 Exposure to Product**

The subjects will be instructed to use the diary to document all doses taken by checking the yes or no box for the appropriate date.

Study drug compliance will be defined as

[Actual number of applications] / [Planned number of applications] \* 100%

where:

- Actual number of applications will be calculated from the subject diary as the number of gel application in the treatment period dosing log.
- Planned number of applications is 112 (28 days, 4 times daily).

Subjects will be considered treatment compliant if they apply at least 75% and not more than 125% of doses.

Duration of exposure will be defined as [Date of last study drug application] – [Date of first study drug application] + 1;

Compliance, actual number of applications and duration of exposure will be summarized descriptively by treatment group for the safety population.

Duration of exposure to the placebo treatment in the run-in period will also be summarized descriptively for the run-in population.

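### As written, the Per Protocol compliance condition in SAP 6.6 excludes on-schedule treatment failures who stop before the end of Day 21, whom the protocol and SAP elsewhere keep in PP with LOCF

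*SAP*

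**What the plan says.** SAP 6.6 builds PP from mITT subjects who satisfy four bullets together.

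- The second bullet is compliance: "apply 75% to 125% (both inclusive) of the scheduled applications of the assigned product". It has no exception and no stated denominator.
- The third asks for a Week 4 evaluation in window. Only here is there an alternative, for subjects who "discontinue from the study due to treatment failure (included as treatment failures").

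Three places indicate what the scheduled number is:

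- SAP 7.12.2: "Planned number of applications is 112 (28 days, 4 times daily").
- Protocol 7.10: "Subjects who will take less than 75% (<84 applications) of total study drug during the study will be considered non-compliant".
- Protocol 12.2.3 item 4: "scheduled doses (e.g., 75% to 125%) of the assigned product for the specified duration of the study".

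Against this, the synopsis says "Patients discontinuing early from the study due to lack of treatment effect will be included in the PP population", and Protocol 12.2.3 item 6 says "Subjects discontinued early from the study due to lack of treatment effect should be included in the PP population", both with LOCF. Item 5 accepts treatment failure in place of the Week 4 visit. SAP 7.10 and 7.11.2 repeat the PP LOCF rule for such subjects. SAP 7.11.3 gives a PP LOCF rule for failures that occur before Week 2. None of these sets a minimum number of applications.

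SAP 7.9 also lists compliance outside 75% to 125%, missing visits and missing WOMAC scores as possible major deviations, without mentioning treatment failure.

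**The concern.** A programmer who derives the PP flag from SAP 6.6 and 7.12.2 would drop most early treatment failures. One who follows Protocol 12.2.3 item 6 or SAP 7.10 would keep them. The definition therefore allows two different populations for the equivalence test, for which PP is definitive.

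If the bullet is applied literally, whether a treated subject counts depends on how early the treatment failed, which is an outcome. If failures are unbalanced between Test and Reference, dropping them can shift the ratio of mean changes.

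**Working it through.** **1. The plan's own limits.** 28 days × 4 = 112; 0.75 × 112 = 84; 1.25 × 112 = 140. These match SAP 7.12.2 and Protocol 7.10.

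**2. When 84 is reached.** Gel starts on Day 1, 4 times daily. Compliance after d full days is 4d/112.

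| Last full day | Applications | % of 112 | Meets bullet |
|---|---|---|---|
| 10 | 40 | 35.7 | no |
| 14 | 56 | 50.0 | no |
| 18 | 72 | 64.3 | no |
| 20 | 80 | 71.4 | no |
| 21 | 84 | 75.0 | yes (inclusive) |

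With imperfect adherence the day is later: 84/3.6 = 23.3, so Day 24 at 90%; 84/3 = 28, so Day 28 at 75%.

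**3. Effect on the Week 2 rule.** SAP 7.11.3 allows PP LOCF for failures before Week 2, from a termination visit up to Day 18. Reaching 84 by Day 18 needs 84/18 = 4.7 applications a day. Under the literal bullet, no on-schedule subject could ever use that rule.

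**4. Illustration of size. The failure inputs are assumed, since the documents give none.** Let r be the Test/Reference ratio among subjects who do not fail, fT and fR the failure proportions, and c the failures' change as a share of the others' change.

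- Ratio if failures are dropped: r.
- Ratio if kept: r × (1 − fT + fT·c)/(1 − fR + fR·c).

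The 90% Fieller limits use zero covariance (SAP 7.11.2.1), Reference mean m_R = 5.85 and SD 4.23 (SAP 3.2), m_T = ratio × m_R, v = SD²/n, and t on 2n − 2 df:

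[m_T·m_R ± √((m_T·m_R)² − (m_R² − t²v)(m_T² − t²v))] / (m_R² − t²v)

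At n = 363, t = 1.647 and t²v = 0.1337. For ratio 1: (34.2225 ± 3.022)/34.0888 = 0.915 and 1.093.

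Assume fT = 5%, fR = 2%, 363 per arm, and every failure early enough to be dropped:

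| r | c | Dropped (90% CI) | Kept (90% CI) |
|---|---|---|---|
| 1.00 | 0 | 1.000 (0.915 to 1.093) | 0.969 (0.886 to 1.060) |
| 1.00 | −0.25 | 1.000 (0.915 to 1.093) | 0.9615 (0.878 to 1.052) |
| 0.95 | 0 | 0.950 (0.867 to 1.040) | 0.921 (0.839 to 1.010) |
| 1.03 | 0 | 1.030 (0.944 to 1.124) | 0.998 (0.914 to 1.091) |

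Every interval lies inside 0.80 to 1.25. In the first three rows dropping failures moves the ratio toward 1; in the last it moves it away. Equal failure rates with zero change give no shift, because the two factors cancel.

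**5. How large an imbalance would matter.** With fR = 2% and c = 0, the lower limit for the kept analysis reaches 0.80 at about 13.6% to 13.8% failures on Test if r = 1, and 9.0% to 9.2% if r = 0.95. At 261 per arm the figures are 12.2% to 12.3% and 7.5% to 7.7%. The ranges reflect whether the Reference mean is itself lowered by its own failures.

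**The case against.** **The denominator is imported.** SAP 6.6 does not cite 112. That figure sits in the exposure section under safety analyses. If the scheduled number meant applications due while on study, an on-schedule failure would be 100% compliant and nothing would conflict. That reading is available, but no passage states it, and Protocol 12.2.3 item 4 points to the full study duration.

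**The intent is plain.** Six or more places keep failures in PP, and a reading that empties an express rule is the less natural one. This is fair, and it is why the point concerns wording to reconcile and not a wrong analysis strategy. It does not make the PP bullet say what is intended.

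**Safeguards exist.** Blind data review finalises the list of excluding deviations, and compliance is on the candidate list in SAP 7.9. ITT and mITT equivalence analyses with LOCF are planned, and SAP 7.1.2 also requires both superiority tests to succeed. These help. But the SAP 6.6 compliance bullet stands apart from the deviation list, and for equivalence the ITT and mITT analyses are sensitivity analyses only.

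**A stronger reading of Protocol 7.10 fails.** A reader might infer that it removes everyone under 84 applications from PP. Its statement that "the same subjects will not be considered for the Per-protocol (PP) population" follows the sentence on more than 140 applications and is clearly tied only to that group. The 84 is used here only as evidence of a full-course count.

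**Conclusion.** The contradiction holds. With the only denominators the documents supply, the SAP 6.6 compliance bullet excludes on-schedule treatment failures who stop before the end of Day 21, while the protocol and the rest of the SAP retain them with LOCF. Day 21 is exact for 4 applications a day and later for lower adherence. A failure with no post-baseline WOMAC score is outside mITT, and so outside PP, in any case.

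The number of subjects affected cannot be computed, because the documents give no failure rate, timing or scores. A reader might infer that the bullet biases the trial toward equivalence or would change its result. The documents support neither: the direction depends on the other subjects' means and on the imbalance in failures, and no case illustrated changes the conclusion. It is worth settling because it defines the decisive equivalence population, and the choice is easy to defend while blinded and hard to defend afterwards.

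**What to change.** Before blind data review:

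- **SAP 6.6:** state that, for subjects discontinued for treatment failure, a shortfall against the 112 planned applications that arises from the discontinuation does not exclude them from PP. Either exempt them from the lower compliance limit, or count only applications scheduled up to discontinuation. The exemption sits closer to Protocol 12.2.3 item 6, which applies no compliance test to them. The second option can still drop a failure who stopped applying some days before removal: for example, 9 days of gel with 13 full days scheduled gives 36/52 = 69.2%. It would also need a rule for the day of removal.
- **SAP 7.9:** state that such a shortfall, or a Week 4 visit or score missing because of treatment failure, is not in itself an excluding deviation.
- **Protocol 12.2.3:** reconcile item 4 with item 6 for analysis-set purposes only. No change to the discontinuation rule in Protocol 7.10 is proposed.

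The cost is a few sentences and a small derivation change. No new data are needed, since Protocol 7.7 already captures the reason for and date of removal. The downside is that PP will contain some subjects with short exposure, as the protocol already intends.

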## **7. STATISTICAL METHODS OF ANALYSIS**

### **7.1 General Principles**

If not otherwise specified, statistical significance is defined as  $p<0.05$  and is two-tailed. No adjustment will be made for multiplicity. Data will be summarized with respect to demographic and baseline characteristics, efficacy variables and safety variables.

For categorical variables, the number and percent of each category within a parameter will be calculated for non-missing data. For continuous variables, statistics will include number of observations, mean, standard deviation, median, minimum and maximum values.

All statistical analyses will be conducted using SAS®, Version 9.3 or higher. Data will be summarized using descriptive statistics for continuous variables. Unless otherwise specified, descriptive statistics will include the number of subjects, mean, standard deviation, minimum, median and maximum. A subset of these statistics may be presented in some tables. The minimum and maximum statistics will be presented to the same number of decimal places as the original data. The mean and median will be presented to one more decimal place than the original data. The standard deviation will be presented to two more decimal places than the original data.

In by-visit summary tables only scheduled visits will be presented. All visits, both scheduled and unscheduled, will be presented in listings.

Baseline will be defined as the last assessment, scheduled or unscheduled, made prior to the first application of the randomized study drug. For subjects who are randomized, but do not receive the randomized study drug, baseline will be defined as the last assessment, scheduled or unscheduled, made prior to the randomization.

### **7.1.1 Derivation of dates**

The start of the run-in period will be taken from the “Run-In Period Day 1 Date” field collected at the “Run-In Period Dosing Log” CRF page.

The end of the run-in period will be derived as the date corresponding to the maximum day recorded at the “Run-In Period Dosing Log” CRF page when gel was applied.

The start of the treatment period, i.e. the date of the first application of the randomized study drug, will be taken from the “Treatment Period Day 1 Date” field collected at the “Treatment Period Dosing Log” CRF page.

For subjects who started the treatment period, the end of the treatment period, i.e. the date of the last application of the randomized study drug, will be taken from the “Date of Last Gel Application” field collected at the “End of Study” CRF page. It must correspond to the maximum day recorded at the “Treatment Period Dosing Log” CRF page when gel was applied or the maximum date recorded at the “Treatment Period Dosing Log (Extended)” CRF page, if any.

Study days will be defined relative to the start of the treatment period. For dates after the start of the treatment period:

Study Day = Date of Assessment – Start of the treatment period + 1

For dates prior to the start of the treatment period:

Study Day = Date of Assessment – Start of the treatment period

All dates will be displayed in DDMMYY format.

### **7.1.2 Adjustment for multiplicity**

The study will test three hypotheses:

1. Equivalence of the Test and Reference treatments
2. Superiority of Test to Placebo treatment
3. Superiority of Reference to Placebo treatment

Possible inflation of Type I error rate will be controlled by declaring the study a success only if all 3 hypotheses are simultaneously true. Therefore there will be no need to apply any multiplicity adjustment methods.

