12.6 Sample Size Considerations

Equivalence between test and reference product⁷

At least 261 subjects in Test Drug and 261 subjects in Reference product will be required to show bioequivalence between Test and Reference product with 90% power and 5% level of significance assuming below estimates:

- 1) 5% difference between Test and Reference of mean change in WOMAC score
- 2) 75 % Inter subject coefficient of variation for Reference in WOMAC Score
- 3) Equivalence margin of 80.00-125.00%

Superiority of test and reference product over placebo

At least 363 number of subjects will be required in each arm to prove the superiority of test/ reference product and placebo product with 90% power and 5% level of significance.

Considering 10% dropout rate, around 1212 subjects would be required to enroll for the study. All Subjects would be randomize in 1:1:1 treatment allocation.

Conclusion: Since the study has two hypotheses viz Equivalence and Superiority, we have chosen the highest sample size.

Test Product: 404 subjects.

Reference Product: 404 subjects

Placebo: 404 subjects

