**Figure 1 Study Design**

### 3.2 Sample Size

The study protocol, MYL-1601N-3002, is designed to demonstrate the Bioequivalence of Diclofenac Sodium Gel to Voltaren® Gel and the superiority of Diclofenac Sodium Gel and/or Voltaren® Gel over Placebo by using a clinical endpoint in patients with Osteoarthritis (OA) of the Knee. The clinical endpoint under consideration is the change from baseline Western Ontario and McMaster Universities Osteoarthritis Index (WOMAC) Likert (version 3.1) pain score. The framework under consideration and the sample size requirements were fine-tuned to satisfy the objectives of bioequivalence of test drug with the reference drug as well as superiority of the test drug to placebo. The sample size estimation is done to ensure 90% statistical power to test two hypotheses of bioequivalence and superiority, the hypotheses are briefly described below:

1. Null Hypothesis (Equivalence) is that the ratio of mean change from baseline in WOMAC Likert pain score between test and reference drug is less than or equal to 0.80 or greater than or equal to 1.25 Vs. the alternative hypothesis of ratio of mean change

from baseline in WOMAC Likert pain score between test and reference drug lies within the limits of 0.80 to 1.25, where the equivalence limit of 0.80 to 1.25 is adapted.

2. Null Hypothesis (Superiority): The mean change from baseline WOMAC Likert pain score of test or reference drug is greater than or equal to Placebo vs the alternative hypothesis of mean change from baseline WOMAC Likert pain score of test or reference drug is less than the placebo group.

To meet the requirement for the two hypotheses, three tests need to be performed to meet overall objectives:

- 1) Bioequivalence between Diclofenac Sodium Gel and Voltaren®
- 2) Superiority of Diclofenac Sodium Gel over Placebo
- 3) Superiority of Voltaren® over Placebo

Sample size calculations are performed under the following assumptions:

1. Mean ( $\pm$  Standard Deviation) reduction from baseline in WOMAC pain score is 5.85 ( $\pm 4.23$ ) for both active treatments.
2. Mean ( $\pm$  Standard Deviation) reduction from baseline in WOMAC pain score is 4.68 ( $\pm 4.89$ ) for placebo.

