### **3.2.2 Superiority of test and reference product over placebo**

At least 363 subjects will be required in each arm to prove the superiority of test/reference drug to placebo with 90% power and 5% level of significance.

Considering 10% dropout rate, around 1212 subjects will be required to enroll in the study. All subjects will be randomized in 1:1:1 ratio.

Overall, to satisfy both hypotheses of equivalence and superiority, the highest sample size will be used in the study: 1212 subjects equally randomized to Test, Reference and Placebo treatments:

1. Diclofenac Sodium Gel: 404 subjects.

2. Voltaren® Gel : 404 subjects
3. Placebo: 404 subjects

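### The 90% power is a per-test figure; with success requiring all three tests, power at 363 evaluable per arm is about 86% to 88% on the documented SDs

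*SAP*

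**What the plan says.** SAP 3.2 acknowledges that "three tests need to be performed to meet overall objectives": equivalence of Test and Reference, Test over placebo, and Reference over placebo. SAP 7.1.2 makes success conditional on all of them, "declaring the study a success only if all 3 hypotheses are simultaneously true", and on that ground applies no multiplicity adjustment. SAP section 5 and Protocol 12.3.2 likewise require both actives to beat placebo.

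The sizing is done one test at a time. SAP 3.2.1 and Protocol 12.6 give 261 per arm for equivalence at 90% power. For superiority, SAP 3.2.2 says: "At least 363 subjects will be required in each arm to prove the superiority of test/reference drug to placebo with 90% power". Protocol 12.6 concludes: "Since the study has two hypotheses viz Equivalence and Superiority, we have chosen the highest sample size". SAP 3.2.2 says that "to satisfy both hypotheses of equivalence and superiority, the highest sample size will be used in the study". SAP 3.2 describes the purpose: "The sample size estimation is done to ensure 90% statistical power to test two hypotheses of bioequivalence and superiority".

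Neither document states a power for the three tests together, or for the two superiority tests together.

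**The concern.** Taking the largest of several single-test sizes guarantees at least the stated power for each test, not for passing all of them. Requiring all three controls type I error, as SAP 7.1.2 says, but the cost falls on power, and the sizing sections do not count it. The main loss is within superiority: two comparisons against one placebo arm must both succeed, so their joint power is below that of either one.

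The power for all three is the quantity that bears on whether the trial meets its own success rule. Someone planning from SAP 3.2 would take 90% as the relevant figure and would find no other.

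**Working it through.** **Inputs.** From SAP 3.2: mean reductions 5.85 (both actives) and 4.68 (placebo), difference 1.17; SDs 4.23 and 4.89. From SAP 3.2.1: CV 75%, which gives an active SD of 0.75 × 5.85 = 4.39 (applied here to both actives, placebo SD kept at 4.89); limits 0.80 to 1.25 with a 90% CI. Superiority tests are two-sided at 5%. Size: 363 evaluable and 404 randomised per arm.

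**1. The plan's own figures.** For superiority, n = (1.960 + 1.282)² × (s_A² + s_P²) / 1.17².
- SD 4.89 in both arms: 368, within 2% of 363.
- SDs 4.23/4.89: 321, which does not match 363.
- The common SD that returns 363 is about 4.86. It is back-solved and appears in neither document.
- Dropout: 363 / 0.9 = 403.3, so 404 per arm and 1212 in total.
- Equivalence: two one-sided tests on the log scale with CV 75% and ratio 0.95 give 90.0% power at 261.

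So the stated sizes can be recovered approximately or exactly, each as a single-test size.

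**2. One superiority test at 363.** Power = Φ(1.17/SE − 1.960), with SE = √((s_A² + s_P²)/363).
- SAP SDs: SE = √((17.893 + 23.912)/363) = 0.3394; 1.17/0.3394 = 3.448; Φ(1.488) = 93.2%.
- Active CV 75%: SE = 0.3448; Φ(1.433) = 92.4%.
- Common SD 4.86: SE = 0.3609; Φ(1.282) = 90.0%.

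**3. Both superiority tests.** The shared placebo arm gives the two statistics a correlation of s_P²/(s_A² + s_P²): 23.912/41.805 = 0.572, then 0.554 and 0.500. The bivariate normal probability of passing both is 88.5%, 87.3% and 83.2%.

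**4. Equivalence alone at 363.** The Fieller criterion is equivalent to one-sided 5% tests on T − 0.8R and T − 1.25R. With the SAP SD, the SE of T − 0.8R is 4.23 × √(1.64/363) = 0.2843, and 0.2 × 5.85 / 0.2843 = 4.115. The upper limit gives the same ratio. Power = 2Φ(4.115 − 1.645) − 1 = 98.6%. The other two cases give 98.0% and 94.7%.

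**5. All three together.** This was simulated with independent arm means and a shared placebo arm (two million draws), actives equal, no covariate adjustment. In the third row below, the 41 subjects per arm outside PP contribute to the superiority tests only.

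| Evaluable per arm | SDs 4.23/4.89 | Active CV 75% | Common SD 4.86 (assumed) |
|---|---|---|---|
| 363 in all analyses | 87.8% | 86.2% | 80.6% |
| 404 in all analyses | 91.6% | 90.3% | 85.8% |
| 404 mITT, 363 PP | 91.1% | 89.7% | 84.4% |

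Multiplying the three powers as if independent (0.932² × 0.986 = 85.6% in the first case) understates the answer because the tests are correlated.

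**6. Unequal actives.** SAP 3.2.1 sizes equivalence for a 5% Test-Reference difference without giving its direction. At 363 with the SAP SDs, the all-three power is about 89% if Test is 5% better and about 69% if it is 5% worse. The large fall comes from Test against placebo, where the difference shrinks to 0.95 × 5.85 − 4.68 = 0.88.

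**The case against.** The strongest reply is that no sentence claims 90% for all three tests. Protocol 12.6, SAP 3.2.1 and SAP 3.2.2 attach 90% to separate calculations, and each of those statements is tenable. The SAP 3.2 sentence can be read as 90% for each hypothesis, and its superiority hypothesis is phrased for Test or Reference. This stands in part. A reader might infer that the plan promises only a 10% chance of failure; the documents do not say that. But the per-hypothesis reading does not rescue the sentence. SAP section 5 defines superiority as both actives beating placebo, and that has 88.5% or 87.3% at 363 on the documented SDs.

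Second, 363 may be too low for superiority. The mITT set with LOCF keeps dropouts who have a post-baseline WOMAC score, so the number lies somewhere up to 404. This stands. With the SAP SDs, about 386 evaluable per arm in every analysis gives 90% for all three tests.

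Third, the planned ANCOVA adjusts for baseline and the calculation does not. This also stands, but the baseline-to-change correlation is not given. As an assumption only, correlations of 0.2 and 0.3 would raise the 87.8% to 89.4% and 91.2%.

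Fourth, the 81% end rests on a back-solved SD. It should not be presented as the plan's own figure.

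**Conclusion.** The point holds. The stated 90% is the power of each test alone, while the success rule needs all three. At the plan's own evaluable number, with equal actives and unadjusted tests, the all-three power is about 88% (SAP SDs) or 86% (75% CV), a shortfall of 2 to 4 percentage points. It is about 81% only under the assumed common SD of 4.86. If mITT keeps 404 and PP has 363, the figures are about 91%, 90% and 84%.

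Equal actives is the SAP 3.2 assumption, not the most favourable case, since a slightly better Test product does marginally better.

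Two stronger conclusions are not supported. One is that the trial is underpowered and needs more subjects: on the documented SDs, retention in mITT alone brings the figure to about 90% or above. The other is that the success rule inflates type I error: it does not.

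Label: wrong as written (stated power).

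**What to change.** In SAP 3.2 and 3.2.2 and Protocol 12.6, state that 90% is the power of each test taken alone. Reword the SAP 3.2 sentence on ensuring 90% power to match. Add the power for all three tests at 363 and at 404 per arm, naming the SDs actually used for 363 and the assumption about the Test-Reference difference.

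The cost is a few lines of text and one power figure that may be slightly less favourable. Do not change enrolment, analyses or the success rule.
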